## Interventions

We have stipulated that the intervention will last three weeks. The first week will be a week of familiarization with the physical tests and protocol, requiring two training sessions, before the initiation of the study to accustom themselves to the physical tests and the protocol procedures. During the first week, the familiarization with the physical tests and the protocol will be performed before the training sessions. The protocol intervention will be performed in the following two weeks, in a total of four training sessions (two per week). The collection of data from the physical tests will begin in the second week, the first moment of collection will be at the at the beginning of first training session and the second moment at the end of the third week (after the fourth protocol session has been completed). The duration of each session will be 20 min.

The intervention protocol proposed in the present study was modified from the protocol used by Aloui et al. (2021), and consists of four sets: (i) First set - 6 hurdle jumps (HJ), with a

distance of 70-cm between each, followed by a 15-m sprint with COD; (ii) Second set - 6 lateral HJ (3 to the left and 3 to the right) followed by a 10-m sprint with COD; (iii) Third set - 6 bouncy strides (BC) followed by a 15-m sprint with COD; (iv) Fourth set - 6 broad jumps (BJ) followed by a 10-m sprint with COD. All COD circuits represent different configurations, changing the sprint distance and the angle of the COD curve. In the last set, we replaced the drop jump with the BJ. Due to the drop jumps being done consecutively, there is a component of horizontal resistance, so we chose to implement the BJ, which offers a greater horizontal component (Dello Iacono et al., 2017) and the forces are generated in the same musculature across the hips, knees, and ankles (Svantesson & Grimby, 1995), being a precursor exercise to improved performance in the sprint and COD (Dello Iacono et al., 2017). All repetitions and sets will be separated by 90-s recovery intervals, as well as, each set will have to be performed 3 times (Aloui et al., 2021). It should be noted that it is intended that the participants perform the procedures under study at the same time of day, i.e., same time and temperature as similar as possible. All physical tests and protocol under study are to be performed with the participants wearing their usual soccer shoes.

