## Methods

### Trial Design

We will perform a randomized parallel trial in a single highly trained female soccer team (highly trained/national level) (McKay et al., 2022) competing in the Portuguese second division. A convenience sample will be used, due to easy access from one of the researchers, who is employed in the club. One group will receive the experimental intervention (EXPG), which will consist of a potentiation protocol as a WU and the second group will receive the control intervention (CONG) which consists of performing their usual WU exercise program. Each group will be tested before and after performing the WU to which they are assigned. Physical tests and intervention protocol will take place during the competitive period. All training sessions and physical tests will be performed on synthetic grass of the team's field. The tests will be applied without a blinded assessor integrating the technical team. However, due to the use of objective and reliable technology, hardly influenced by knowledge of the interventions to which the participants were allocated, we are confident that the non-blinded of assessors will not have a meaningful impact on the results.

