## Participants

Eighteen female soccer players between 16 and 21 years of age will participate in this study. Participants will be randomly allocated between a CONG (n=9) and a EXPG (n=9), using the Excel Software and the Random function and the allocation sequence will be concealed from the main researcher, responsible for the implementation of the protocols, until the beginning of the interventions. The inclusion criteria, to be applied before the randomization process, will consider athletes, from any playing position (except goalkeepers), able to train without limitations. Subjects will be excluded if they have any existing medical conditions that will compromise their participation. All participants will be informed about the purpose and content of the project, as well as the potential risks and benefits of the study, and will sign an informed consent.

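### Week 1 rehearses the experimental protocol before the baseline test, with the recipients unstated and the end of concealment not tied to the pre-test

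*Combined protocol and SAP*

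**What the plan says.** Under Interventions, the opening week covers both the tests and the protocol: "The first week will be a week of familiarization with the physical tests and protocol, requiring two training sessions". The same sentence places this week "before the initiation of the study to accustom themselves to the physical tests and the protocol procedures". Yet the section opens with "We have stipulated that the intervention will last three weeks", a count that is reached only by including week 1.

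The treatment sessions follow: "The protocol intervention will be performed in the following two weeks, in a total of four training sessions (two per week"). For measurement, "The collection of data from the physical tests will begin in the second week", at the start of the first session, and the post-test is "the second moment at the end of the third week (after the fourth protocol session has been completed").

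Under Participants, "the allocation sequence will be concealed from the main researcher, responsible for the implementation of the protocols, until the beginning of the interventions". Nothing is said about concealment from the players or from the assessor, whom Trial Design describes as unblinded and part of the technical staff. Trial Design also defines the comparator: "the second group will receive the control intervention (CONG) which consists of performing their usual WU exercise program".

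The plan does not state who rehearses the protocol in week 1, whether rehearsal means full or partial sessions, or whether allocation is still sealed when the pre-test is run.

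**The concern.** A pre-post comparison of two warm-ups needs controls who have not had the experimental warm-up, and a baseline taken before exposure and before anyone involved knows the allocation. The text does not secure these together.

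- **Interventions start in week 2.** The researcher who delivers the protocols does not know the allocation in week 1 and cannot restrict rehearsal to one group. Both groups, including the 9 controls, would practise the experimental protocol before baseline.
- **Interventions start in week 1.** Only the experimental group need rehearse. Its baseline is then measured after exposure, and allocation is known when the baseline is run.

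Carry-over is plausible on the plan's own description. The protocol consists of jumps followed by 10-m and 15-m sprints with change of direction, and the outcomes are a change-of-direction test and a 40-m sprint, so rehearsing one resembles practising the other. The T-test section allows a single attempt because of limited time. The assurance in Trial Design about objective timing equipment covers measurement; it does not cover how hard a player runs once she knows her group.

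At stake is the group-by-time contrast, which is the natural test of the stated hypothesis (the Statistical analysis section names the mixed ANOVA but not the term of interest).

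**Working it through.** The plan gives no sample-size calculation, effect size or standard deviation, so there is no figure of its own to reproduce. What follows is an illustration.

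**Inputs from the documents.** 9 players per group; 2 familiarisation sessions before baseline; 2 weeks × 2 sessions = 4 protocol sessions between the two tests; significance level 0.05.

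**Assumptions, not in the documents.** Two-sided test. Each rehearsal counts as a full session (an upper bound, since the amount is unstated). Any gain persists to the post-test. Let f(k) be the lasting gain after k protocol sessions.

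**Step 1: the contrast with and without rehearsal.**
- Plan, both groups rehearse: experimental change f(6) − f(2), control change f(2) − f(2) = 0.
- Plan, experimental group only: experimental change f(6) − f(2), control change 0.
- No protocol rehearsal in week 1: experimental change f(4), control change 0.

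The share of the contrast kept under the plan is therefore [f(6) − f(2)] / f(4) on both readings.

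**Step 2: apply response curves.**
- Linear, f(k) = ck: (6c − 2c) / 4c = 1.00. No loss.
- Purely acute effect: week-1 practice leaves nothing behind, so the share is 1.00. No loss.
- Saturating, f(k) = 1 − exp(−k/τ), with τ in sessions: the numerator is exp(−2/τ) − exp(−6/τ) = exp(−2/τ) × [1 − exp(−4/τ)], so the share reduces to exp(−2/τ).

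**Step 3: translate into power.** For a two-sample t-test with 9 per group (16 df, critical value 2.12, noncentrality d × √(9/2)), 80% power needs d = 1.41 SD of whatever is compared, here the change. Take an effect of that size without rehearsal and shrink it by the share:

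| τ (sessions) | Share = exp(−2/τ) | Effect = 1.41 × share | Power |
|---|---|---|---|
| 6 | 0.72 | 1.01 SD | about 52% |
| 4 | 0.61 | 0.85 SD | about 40% |
| 2 | 0.37 | 0.52 SD | about 18% |

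If each rehearsal counts as half a session, the two together equal one session and the share becomes exp(−1/τ): 0.85, 0.78 and 0.61 for the same τ.

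**Step 4: can the bias run the other way?** If both groups rehearse and the controls lose their early gain by the end of week 3, the control change is −f(2) and the contrast becomes f(6). The ratio f(6)/f(4) is 6/4 = 1.5 for the linear curve, and 1.30, 1.23 and 1.10 for τ = 6, 4 and 2. In that case the contrast grows.

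**The case against.** The strongest reply is that the text, read as a whole, describes ordinary familiarisation. Week 1 is said to precede the study, the protocol intervention is placed in the two weeks after it, and baseline is taken at the start of the first of those sessions. On that reading both groups get the same preparation, the randomised comparison stays balanced, and exposure after baseline is 4 sessions against 0. Becoming accustomed to procedures need not mean full sessions. The Introduction's rationale is acute, with a peak 7-10 minutes after the conditioning activity, and such an effect cannot carry over from week 1. Practising the tests beforehand is an advantage when a test is attempted once.

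Much of this stands. Starting in week 2 is the more natural reading, test familiarisation should stay, and two full sessions is an upper bound on rehearsal. Two gaps remain. Nothing keeps allocation sealed until the pre-test is finished, since concealment covers one person and ends at an event the section dates inconsistently. And the tests bracket two weeks of sessions, so any lasting effect enters the planned contrast.

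A reader might infer that the contrast is diluted whichever way the plan is followed, or that one third of the effect is lost because 2 of the experimental group's 6 exposures precede baseline. The documents do not support either. With even accrual per session, the plan and a plan without rehearsal both deliver 4 sessions' worth of contrast, and a purely acute effect is untouched.

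**Conclusion.** The point holds as a possible bias together with an inconsistency that must be reconciled; it does not show that dilution will occur. The text establishes that protocol practice precedes baseline, that its recipients and amount are unstated, and that the end of concealment is not fixed relative to the pre-test.

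The likely direction is toward no effect, but only if the effect lasts and has diminishing returns. Under the assumed saturating curve with full-dose rehearsal and retained gains, the loss runs from about 28% (τ = 6) to 63% (τ = 2) of the contrast. It is zero under linear accrual or a purely acute effect, and the sign reverses if rehearsed controls lose their gain. If only the experimental group rehearses, the damage is to the change from baseline; a post-test-only comparison would not be diluted. Effort influenced by knowledge of allocation at baseline could push the result either way.

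It would also go too far to say that a null result could not be interpreted. It would be harder to interpret to the extent that a lasting, saturating effect is credible, and 9 per group gives limited precision in any case. The change is still worth making, because it removes the ambiguity at almost no cost.

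**What to change.** Change Participants and Interventions as follows.

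1. Limit week-1 familiarisation to the two physical tests, for all 18 players.
2. State that allocation stays sealed from the researcher, the assessor and the players until the last pre-test time has been recorded.
3. Introduce the protocol to the experimental group only after that point.
4. Reconcile the two sections on when the intervention begins: either week 1 is part of it or it is not, and the end of concealment should be tied to completion of the pre-test and not to the start of the interventions.

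The cost is a few sentences, with no extra players, sessions or staff. The downside is small but real: the experimental group will be less practised at the first of its four protocol sessions.

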## Outcomes

### T-test

Pre-planned COD will be assessed through the T-test (Krolo et al., 2020), and applied according to standardized procedures described elsewhere (Miller et al., 2006). However, forcing the participant to touch on each cone is not uniform (Raya et al., 2013), and this step will be withdrawn. We will implement course directions used previously (Miller et al., 2006). The validated and reliable WICHRO® Wireless photocell system (Chronojump®), which consists of two pairs of barriers containing the photocell and its double reflector, will be used (López-Samanes et al., 2020), and the test will start and end on the same pair of barriers. Each player will perform each test once due to the time limitation for collecting the test data.

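### The group comparison rests on one pre-test and one post-test run per player; baseline adjustment, with eligible week-1 runs averaged in, could make it more precise

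*Combined protocol and SAP*

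**What the plan says.** Under Outcomes, the T-test section states: "Each player will perform each test once due to the time limitation for collecting the test data". The wording covers each test, so I read it as applying to the 40-m sprint too; that section gives no number of runs.

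The Interventions section sets two collection moments: the start of the first session in week 2, and "the second moment at the end of the third week (after the fourth protocol session has been completed". On week 1 it says: "The first week will be a week of familiarization with the physical tests and protocol, requiring two training sessions". It adds that "the familiarization with the physical tests and the protocol will be performed before the training sessions", and then: "The collection of data from the physical tests will begin in the second week". Week-1 results are therefore not planned as data.

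The Statistical analysis section plans a mixed repeated measures ANOVA with within- and between-player factors. The Participants section fixes the size: "Eighteen female soccer players between 16 and 21 years of age will participate in this study", nine per group. No power calculation, standard deviation or test-retest figure is given. The error of ±0.001 s in the sprint section is that of the timing device, not of the player.

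**The concern.** With one run before and one after, a player's change contains the error of both runs. The sample is a convenience sample from one team, so recruiting more players is not an easy remedy. The analysis and the quality of the baseline are among the few things that can still be improved.

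Two resources are not used. The pre-test could be a covariate instead of being subtracted. And if players complete full runs of the tests in week 1, those runs could be timed and averaged into the baseline without a second run on a study test day.

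The Introduction also expects a meaningful improvement, but the plan has no figure for a player's normal run-to-run variation against which to judge one. Repeated baseline runs would supply it.

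**Working it through.** The plan gives no precision figure to reproduce, so this compares analyses under stated assumptions.

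**Inputs.** From the documents: 9 players per group, one run per test at each of two moments, significance at 0.05 (taken as two-sided). Assumed: a correlation ρ of 0.7 to 0.9 between any two runs of one player, equal variance across runs, and one full timed run in one or both week-1 sessions.

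**Step 1: the planned test.** With two moments, the group-by-time test equals a t-test on change scores with 16 degrees of freedom. Nine per group detects 1.41 SD of the change score with 80% power.

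**Step 2: variances**, in units of the single-run variance.
- Change score: 2(1 − ρ).
- ANCOVA on the mean of k baseline runs: 1 − kρ²/(1 + (k − 1)ρ).

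| ρ | Change score | ANCOVA, k=1 | k=2 | k=3 |
|---|---|---|---|---|
| 0.7 | 0.600 | 0.510 | 0.424 | 0.388 |
| 0.8 | 0.400 | 0.360 | 0.289 | 0.262 |
| 0.9 | 0.200 | 0.190 | 0.147 | 0.132 |

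**Step 3: ANCOVA on the week-2 run alone.** The residual variance falls by 15% (0.510/0.600), 10% (0.360/0.400) or 5% (0.190/0.200). Two small-sample costs offset this. One degree of freedom is lost (16 to 15), and chance imbalance in the covariate inflates the variance by 1 + 1/(18 − 4) = 15/14, on average about 7%. The variance ratios to the change score become 0.85 × 15/14 = 0.91, 0.90 × 15/14 = 0.96 and 0.95 × 15/14 = 1.02. A simulation of 40,000 trials at ρ = 0.8 agrees: the SD of the group contrast was 0.2930 for ANCOVA and 0.2985 for the change score, and (0.2930/0.2985)² = 0.96. So the net gain is about 9% at ρ = 0.7, 4% at 0.8, and a loss of about 2% at 0.9.

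**Step 4: averaging in week-1 runs.** Relative to ANCOVA with k=1, the variance falls by 17%, 20% and 22% with one extra run, and by 24%, 27% and 30% with two. The 15/14 factor is common to both sides and cancels. At ρ = 0.8 this is worth 18 × 0.360/0.289 ≈ 22 players, or 18 × 0.360/0.262 ≈ 25. The simulation gave an SE ratio of 0.853 for k=3, a variance ratio of 0.73.

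**Step 5: both steps together at ρ = 0.8, k=3.** Against the plan, 0.262/0.400 × 15/14 = 0.70, a cut of about 30%. The difference detectable with 80% power falls from 1.41 × √0.400 = 0.89 to 1.413 × √0.262 × √(15/14) ≈ 0.75 single-run SDs.

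**Step 6: when the averaging gain disappears.** Suppose players differ in how much they learn, which adds variance to the week-1 runs equal to c times the single-run error variance. The error variance of the three-run mean, relative to one week-2 run, is (3 + 4c)/9 if both week-1 runs share the extra part and (3 + 2c)/9 if it is independent. These equal 1 at c = 1.5 and c = 3. At ρ = 0.8 the error variance is 0.2, so a week-1 run then has variance 1.3 or 1.6, and its correlation with the post-test is 0.8/√1.3 = 0.70 or 0.8/√1.6 = 0.63. Below those values the simple mean is worse than the week-2 run alone. A learning shift common to all players does not move the group contrast.

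**The case against.** The strongest objection is factual. A reader might infer that the tests are already run and timed in week 1, that the readings are thrown away, and that using them costs no extra runs. The documents do not support that. They speak only of familiarisation, with no number of runs, effort level or timing. If practice is partial, full runs would have to be added. Timing 18 players on two tests also takes set-up and recording time, and time is the constraint the plan itself cites.

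A reader might also infer that week-1 runs cannot bias the comparison because they precede allocation. The documents do not place randomisation after week 1. The Participants section says only that the sequence is concealed from the main researcher until the interventions begin, and the Interventions section counts familiarisation as the first of three weeks. Week 1 also includes practice of the protocol, and the plan does not say who practises it or whether test runs come first. A run made after exposure that differs by group would not be a clean baseline.

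Finally, familiarisation exists because early runs are unstable, so equal correlation is a favourable assumption. And familiarising players before taking one standardised baseline is a coherent design.

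All of this stands. It makes the week-1 part conditional. It does not touch the facts that each value is one run and that the planned test is a change-score test.

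**Conclusion.** The point holds as an optional improvement with conditions. The ANCOVA step needs no new data, but its net gain in 18 players is small: about 9% less variance at ρ = 0.7, and none at 0.9. Its other merit is that the slope is estimated from the data, so a poorly correlated baseline is not given full weight.

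The larger gain would come from averaging. It depends on full, timed, eligible week-1 runs existing, and on their correlating with the post-test about as well as the week-2 run does. Neither the number of such runs nor any correlation is in the documents. The statements that no runs are added and that no bias arises therefore hold only under the eligibility conditions below. The post-test remains a single run, so its own error is untouched.

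**What to change.** 1. In Statistical analysis, make the primary group comparison for each test an ANCOVA of the post-test time adjusted for the week-2 pre-test time.
2. In Interventions, state how many full runs of each test are made in week 1, where they fall relative to protocol practice, and when allocation is made and disclosed.
3. Where full week-1 runs are made, time them with the existing photocells. Under a rule fixed before data are seen, use the mean of the eligible week-1 times and the week-2 time as the covariate. Eligible runs are those done before any protocol exercise, in the same way in both groups, and before allocation is known. If none qualify, use the week-2 time alone.
4. Keep the week-2 run identifiable and use it for any within-group change, since averaging in learning runs would distort that change.
5. Report the week-1 to week-2 typical error (SD of the differences divided by √2) as a yardstick for meaningful change, noting that learning may inflate it.

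The cost is a few sentences of text plus photocell set-up and recording time in week 1. Study test days stay at one run per test. The remaining risk is that learning shrinks or reverses the averaging gain, so an analysis with the week-2 run alone should be reported alongside.

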### 40-m linear sprint

The same WICHRO® Wireless photocell system will be used for the 40-linear sprint (Iruetia et al., 2022). The time will be counted in seconds and thousandths of a second (ms) with an error of  $\pm 0.001$ s (Sánchez-Pay et al., 2021). After a 5 s countdown, the participants run forward following the route marked by cones, one at 0m indicating the start place and the other at 40m indicating the finish place. Participants will start the test from a standing start position with the front foot approximately 2 cm behind the first cone.

### Statistical analysis

An intention-to-treat analysis will be performed. The normal distribution will be verified by the Shapiro-Wilk test. The statistical analysis will involve descriptive and inferential statistics, and data will be presented by mean  $\pm$  standard deviation. Then, a mixed repeated measures ANOVA (i.e., within- and between-factors) will be used. The assumption of sphericity will also be analyzed. Effect sizes will be calculated using partial eta squared ( $\eta_p^2$ ) and will be classified as small (0.010-0.059), moderate (0.060-0.137), and large ( $>0.137$ ) (Cohen, 2013). Statistical significance will be assumed at  $p < 0.05$ . Statistical analysis will be performed using the IBM SPSS (*Statistical Package for the Social Sciences*) version 27.

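### If any player misses a test, the named pre/post ANOVA becomes a complete-case analysis and no longer delivers the promised intention-to-treat analysis

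*Combined protocol and SAP*

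**What the plan says.** The Statistical analysis section makes two statements that have to be read together: "An intention-to-treat analysis will be performed", and "a mixed repeated measures ANOVA (i.e., within- and between-factors) will be used". It adds that "The assumption of sphericity will also be analyzed". It names SPSS version 27 but not the procedure.

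The Participants section gives the sample: "Eighteen female soccer players between 16 and 21 years of age will participate in this study", nine per group. The Interventions section sets two collection moments: the start of the first session in week two, and the end of week three after the fourth session. The T-test section allows one attempt per test, so a missed occasion has no backup value. On timing, the Trial Design section says: "Physical tests and intervention protocol will take place during the competitive period".

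The documents do not define the intention-to-treat set. They contain no rule for a player who misses a test, no imputation, no sensitivity analysis and no dropout allowance.

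**The concern.** A reader told that the analysis is intention-to-treat will take it that all 18 randomised players are analysed in their allocated group. A pre/post ANOVA cannot guarantee that, because a player with only one of the two values has no change and adds nothing to the group-by-time test. The word mixed does not rescue the plan. The text explains it as within- and between-factors and adds a sphericity check, which describes a split-plot ANOVA and not a likelihood-based mixed model.

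Each lost player is 1/9 = 11% of an arm. Without a rule fixed in advance, who counts as analysed would be settled after the data are seen. If loss differs by arm and depends on baseline speed, the complete-case change contrast is also biased, and a model that uses the baseline values avoids that bias.

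**Working it through.** **Inputs from the documents.** 18 players, 9 v 9 (Participants); two measurement times (Interventions); one attempt per test (T-test); significance level 0.05, taken as two-sided (Statistical analysis). The trial uses a convenience sample with no stated power, effect size, SD or dropout, so there is no sample-size figure to reproduce beyond 9 + 9 = 18.

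**Assumed inputs.** Missingness per player of 2% to 10%; pre-post correlation ρ of 0.5 to 0.9; equal SD at both times.

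**1. Who enters the test.** With two time points, the group-by-time F equals the squared two-sample t on post minus pre. In a simulated 9 v 9 data set with two post-tests removed:
- the split-plot F was 3.182 and the squared t was 3.182, both on 16 players (error df 14);
- altering the baselines of the two incomplete players left F unchanged, so they contribute nothing;
- a linear mixed model with the same terms used all 18 players and 34 observations.

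**2. How likely the conflict is.** P(at least one of 18 misses a test) = 1 − (1 − p)^18, if misses are independent:

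| Assumed p | P(at least one) |
|---|---|
| 2% | 30% |
| 5% | 60% |
| 10% | 85% |

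**3. Bias when loss depends on baseline speed.** Suppose the two slowest EXPG players at baseline miss the post-test.
- The two largest of nine standard normal values have expectations 1.485 and 0.932, so the remaining seven average −(1.485 + 0.932)/7 = −0.345 SD at baseline.
- They regress towards the mean, so their expected change is shifted by (1 − ρ) × 0.345, in SDs of a single test time.
- ρ = 0.5: 0.17. ρ = 0.8: 0.07. ρ = 0.9: 0.035.
- Simulation (40,000 runs each) gave 0.175, 0.069 and 0.035 for the change contrast. Baseline-adjusted estimation, which is close to the common-baseline mixed model, was within 0.004 of zero.
- The sign is positive on the time scale, so EXPG looks slower than it should.

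**4. Bias when loss depends on the unseen change.** If 2 of 9 EXPG players are lost and would have changed 1 SD less favourably than the other seven, the EXPG mean is overstated by 2/9 × 1 = 0.22 SD. In simulation, the complete-case and baseline-adjusted estimates were both biased by 0.22 SD at ρ = 0.5, 0.8 and 0.9.

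**5. Power.** Take an effect of 1.41 SD of change, chosen only because it gives 80% at 9 v 9. Noncentral-t power is then 77% at 9 v 8 and 74% at 9 v 7. A player with only a baseline adds little information on the contrast under either model, so this fall is the price of the missing data.

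**6. Precision with complete data.** The ratio of the baseline-adjusted standard error to the change-score standard error is √[(1 + ρ)/2 × 15/14], where 15/14 allows for estimating the slope with 18 players.
- ρ = 0.5: √(0.75 × 1.071) = 0.90.
- ρ = 0.8: √(0.90 × 1.071) = 0.98.
- ρ = 0.9: √(0.95 × 1.071) = 1.01.

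**The case against.** The strongest reply is that this is an omission, not a contradiction. Intention-to-treat also means analysing players in the group assigned whatever sessions they attended, and the ANOVA allows that. It also does not forbid imputing before analysis, and no deletion rule is written down. The study is short, in one team, and no document reports or expects missed tests. All of this is correct, and it makes the point conditional. It does not remove the point, because no imputation or other rule is given, and without one the named test leaves incomplete players out.

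Three stronger readings are tempting, and the documents do not support them.

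- **That the analysis will be complete-case.** This holds only if a test is missed. With 18 complete pairs, complete-case and intention-to-treat coincide.
- **That losses would favour the experimental warm-up.** Nothing in the documents says who would be lost. Losing the slower EXPG players at baseline biases the change contrast against EXPG (step 3). Only loss tied to poor change favours it (step 4).
- **That the 0.22 SD bias or the power loss is the cost of choosing ANOVA.** The 0.22 SD arises under a missing-not-at-random assumption and affects the mixed model equally. The power loss comes from the lost data.

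It is also fair to object that the replacement model changes the estimate even with nothing missing. A common-baseline model gives a baseline-adjusted difference, which is not numerically the ANOVA interaction. Under randomisation both target the same effect.

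**Conclusion.** The point holds in conditional form. The plan promises intention-to-treat and names a method that covers all randomised players only if every one of them completes both tests. The chance that this fails is 30% to 85% for assumed missingness of 2% to 10% per player.

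The part of the harm that a better model removes is the bias from baseline-dependent loss that differs by arm. That is about 0.035 to 0.17 SD if the two slowest EXPG players are lost and ρ lies between 0.9 and 0.5. Bias from loss tied to unobserved change stays under either model and can only be probed by a sensitivity analysis. The missingness rates, correlations and loss patterns are all assumptions, since the documents state none.

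**What to change.** In the Statistical analysis section:

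1. Define the intention-to-treat set as all randomised players, analysed in their allocated group.
2. Replace the ANOVA with a linear mixed model (SPSS MIXED, REML, small-sample degrees of freedom) on every recorded time, with a common baseline mean. The estimate is the group difference at post-test.
3. Add one sensitivity analysis that gives any player without a post-test, in either arm, her own pre-test value.
4. Report the numbers randomised and analysed per arm for each test.

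The cost is a change of wording and a few lines of syntax in the software already named, with no new data. There are two downsides. The model assumes missing at random, hence the sensitivity analysis. Its estimate and p-value will also differ from the ANOVA interaction even with complete data, though it targets the same effect. Its precision ranges from about 10% better at ρ = 0.5 to equal within 1% at ρ = 0.9. The change should be made before any results are seen.
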